#### 5.6 Previous Clinical Experience with Other ChAdOx1 Vaccines

A number of other ChAdOx1 vectored vaccines have also been developed and tested in clinical trials, most notably the ChAdOx1 nCoV-19 (Oxford/AstraZeneca COVID-19 vaccine) which has been approved in many countries with over 2 billion doses administered worldwide. 

Early phase clinical trials have also been performed for a number of other ChAdOx1 vectored vaccines for Influenza (encoding the fusion protein NP+M1), Tuberculosis (85A), prostate cancer (5T4), Malaria (LS2), Chikungunya (structural polyprotein), Zika (prM and E), Group B Meningococcus (outer membrane protein), Middle East Respiratory Syndrome Coronavirus (spike protein), Ebola (Zaire and Sudan surface glycoproteins) and others, with positive safety and immunogenicity results. Further details of other ChAdOx1 clinical studies are contained within the ChAdOx1 NipahB Investigator Brochure.

RECRef: 23/SC/0268 NIV001: A study of a new vaccine against Nipah Page 23 of 71

#### 5.7 Rationale for Selected Doses

The regimen and dose of ChAdOx1 NipahB (5 x  $10^{10}$  viral particles per dose, as either a single or two-dose administration) was selected on the basis of pre-clinical and clinical experience with other ChAdOx1 vaccines, as well as other adenovirus vaccines.

The ChAdOx1 NipahB pre-clinical toxicology study (Labcorp 850643, carried out using the engineering batch, summarised in the ChAdOx1 NipahB Investigator's Brochure) supports the clinical evaluation of ChAdOx1 NipahB in a two dose 12-week schedule as in this clinical trial, in line with WHO guidelines on non-clinical evaluation of vaccines. BALB/c mice were administered 1 x 10^10 IM of ChAdOx1 NipahB with a 2-week dose interval and a 2-week recovery period. This dose was well tolerated and not associated with any clinically important treatment-related adverse effects.

Seventeen ChAdOx1 vectored-vaccines expressing different immunogens have been administered in clinical trials at doses ranging from  $5 \times 10^8$  to  $5 \times 10^{10}$  (the maximum dose tested). A summary of these trials is listed in the appendix of the ChAdOx1 NipahB Investigator's Brochure. Recent phase 1 clinical trials of ChAdOx1 vaccines for Ebola, MERS, Chikungya, Zika and Rift Valley Fever have each included participants immunised with  $5 \times 10^{10}$  viral particles (following dose escalation within each of these trials). In every case, the safety and immunogenicity profiles were acceptable for the  $5 \times 10^{10}$  viral particle dose, including when this dose was given as a two-dose regimen as in the EBL07 ChAdox1 biEBOV phase 1 trial.

ChAdOx1 nCoV-19 has been approved as a 2-dose schedule, administered 4 to 12 weeks apart, at a dose of 5 x 10^10 viral particles per dose (or equivalent). This regimen is well tolerated and immunogenic. Although approved as a 2-dose schedule, the vaccine is immunogenic following the first dose. Experience with ChAdOx1 nCoV-19 showed that the second dose significantly boosts binding and neutralising antibody responses to SARS-CoV-2. A 12-week interval between doses results in superior immunogenicity to a 4-week interval. The second dose produces lower rates of adverse reactions compared to the initial dose. Real-world studies have demonstrated efficacy following a both a single and two-dose regimen.

Another simian adenovirus vector (ChAd63) has been safely administered at doses up to  $2 \times 10^{11} \text{ vp}$  with an optimal dose of  $5 \times 10^{10} \text{ vp}$ , balancing immunogenicity and reactogenicity.

The African green monkey challenge study described above in section 5.3.2 included a prime-only and prime-boost regimen (28 days apart) of  $2.5 \times 10^{10}$ . This demonstrated evidence of boosting following the second vaccine dose, with all animals (both in the prime-only and prime-boost groups) protected from clinical disease.

Based on these data, this study will include both a single and 2-dose regimen of ChAdOx1 NipahB, each containing  $5 \times 10^{10}$  viral particles. The 2-dose regimen incorporates a 12-week interval between doses. It is important to investigate the immunogenicity following one dose, as this vaccine could be used in a reactive outbreak setting where a single dose, able to elicit rapid and sufficient protective immunity, would be ideal. The vaccine could also be given in a preventive context, where a two-dose schedule may be required to stimulate longer-lasting immunity. It is important compare the immune responses between a single and 2-dose schedule for these reasons.

RECRef: 23/SC/0268 NIV001: A study of a new vaccine against Nipah Page 24 of 71

#### 5.8 Potential Risks to Participants

Trial related risks are summarised below. Potential risks associated with ChAdOx1 NipahB are also discussed in further detail within the ChAdOx1 NipahB Investigator's Brochure.

### 5.8.1 ChAdOx1 NipahB-Related Risks

The most likely side effects that recipients of ChAdOx1 NipahB may experience are short-lived local reactions (primarily injection site tenderness or pain) and systemic reactions (fatigue, headache, malaise, feverishness) that resolve completely within days.

Very rare serious reactions have been identified as part of post-marketing surveillance of ChAdOx1 nCoV-19 (Oxford/AstraZeneca COVID-19 vaccine). These include thrombosis with thrombocytopenia (TTS), immune thrombocytopenic purpura (ITP), Guillain-Barré syndrome (GBS), transverse myelitis, capillary leak syndrome (CLS), and anaphylaxis. It is currently unknown whether these very rare reactions occur with other ChAdOx1 vaccines. As ChAdOx1 NipahB is similar to ChAdOx1 nCoV-19, participants will be informed about these conditions as part of the informed consent process for the trial. Investigators will be aware of potential signs of these conditions.

Given existing safety data which supports the use of ChAdOx1 nCoV-19 use in pregnant women, there is no reason to believe ChAdOx1 NipahB would be harmful to women or the foetus during pregnancy. However, as yet there are no data on the use of ChAdOx1 NipahB in pregnancy. Therefore, pregnant women will be excluded from the trial and women of childbearing potential will be required to use effective contraception to take part (section 8.4).

#### 5.8.2 Other Trial-Related Risks

Blood sampling during the trial may cause slight pain, bruising, light-headedness or fainting. The volume of blood given in the trial is less than that taken by regular blood donors over the same period, so should not compromise healthy participants. Intramuscular injections carry a risk of bleeding in patients with very low platelet counts or coagulopathies. A baseline full blood count (with a platelet count) taken prior to vaccination reduces this risk.

The medical tests carried out during the trial screening and follow up have the potential to find incidental medical problems that may require referral of participants for further investigation. Participants will be informed of these and, with their consent, their general practitioner (GP) will be contacted.

### 5.9 Potential Benefits to Participants

The recruitment population will not directly benefit from participation in the study. This is because the individual's risk of becoming infected with NiV is currently low. Furthermore, ChAdOx1 NipahB clinical efficacy against NiV infection has not been established, and will not be established by this study. Participants will be informed that they should not anticipate any protection from potential future NiV infection following participation in this study. No specific additional medical care will be provided through participation, and medical procedures are performed with the aim of determining eligibility and safety during the trial.

RECRef: 23/SC/0268 NIV001: A study of a new vaccine against Nipah Page 25 of 71

### **6 OBJECTIVES AND ENDPOINTS**

# 6.1 Objectives, Outcome Measures and Evaluation Timepoints

Outcome	Objective	Outcome measure	Evaluation timepoints 
Primary	To assess the safety and tolerability of ChAdOx1 NipahB in healthy volunteers aged 18-55	a) Occurrence of solicited local reactogenicity signs and symptoms b) Occurrence of solicited systemic reactogenicity signs and symptoms c) Occurrence of unsolicited adverse events (AEs) d) Occurrence of abnormal safety laboratory measures	7 days following each vaccination
		e) Occurrence of serious adverse events (SAEs) and adverse events of special interest (AESIs)	Cohort 2 : D0, D1, D14, D28, V2, V2+1, V2+14, V2+28 Duration of the study (D0 to V2+281)
Secondary	To assess the immunogenicity of ChAdOx1 NipahB vaccine in healthy adult volunteers aged 18-55	NipahB glycoprotein G-specific serological response as measured by ELISA	Cohort 1: D0, D14, D28, D56, V2, V2+14, V2+28, V2+56, V2+281 Cohort 2: D0, D14, D28, V2, V2+14, V2+28, V2+281
Exploratory 	Immunological profiling	a) NipahB neutralising antibody responses measured by live or pseudoneutralisation assays b) NipahB glycoprotein G T cell response measured by IFN-g ELISPOT c) Cellular immune response to Nipah virus measured by ICS, proliferation and/or whole blood assays	Timepoints will be detailed in the laboratory analysis plan
	To assess anti-PF4 antibody levels following vaccination	Change in anti-PF4 antibody level measured by ELISA	D0, D14, V2+14
	To assess anti-vector immunity following vaccination	Binding and/or neutralising antibody responses against ChAdOx1	Timepoints will be detailed in the laboratory analysis plan

Visit and procedure timepoint windows are defined in section 4 (Schedule of Procedures). These exploratory endpoints may be performed; additionally, sample analysis for the completion of exploratory endpoints may be performed under the ethically-approved Oxford Vaccine Centre (OVC) Biobank protocol (REC 21/SC/0161). Further exploratory assays/analyses may be carried out (see section 9.6.2).

RECRef: 23/SC/0268 NIV001: A study of a new vaccine against Nipah Page 26 of 71

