# 4.3 Schedule of Procedures Table: Vaccination and Follow up Visits (Cohort 2)

Table 3 Schedule of Procedures Table: Vaccination and Follow up Visits (Cohort 2)

Visit Number	1	2	3	4	5	6	7	8	9
Visit type	Vac1	f/u	f/u	f/u	Vac2	f/u	f/u	f/u	f/u
Timeline 	D0	D1	D14	D28	V2 (D84)	V2+1	V2+14	V2+28	V2+281
Time window (days)		+1	±3	±3	±14	+1	±3	±3	±60
Visit Procedures									
Review contraindications, inclusion and exclusion criteria	Х				х				
Randomisation	Х								
Vaccination (and immediate post-vaccination observation period)	Х				Х				
Vital signs (heart rate, temperature, blood pressure)	Х	Х	Х	х	Х	Х	Х	Х	
Targeted medical history/physical examination, if required	(X)	(X)	(X)	(X)	(X)	(X)	(X)	(X)	(X)
Adverse Event Collection									
Solicited AE collection	D0 t	o D6			V2 to V2	2+6 days			
Unsolicited AE collection		D0 to	D27			V2 to V2	+27 days		
SAEs & AESI collection	Х	Х	Х	Х	Х	Х	Х	Х	Х
Review ongoing AEs		Х	Х	Х	Х	Х	Х	Х	Х
Electronic diary (eDiary) 									
Electronic diary started	Х				Х				
Electronic diary review (in clinic)		Х	Х	Х		Х	Х	Х	
Electronic diary closed				Х				Х	
Urine Samples									
Highly Sensitive Urinary hCG (WOCBP only)	Х				Х				Х
Blood Samples 									
HLA typing (mL)	~4								
Biochemistry, Haematology (mL) [LFTs, U+Es, FBC]	~5	~5	~5	~5	~5	~5	~5	~5	
Immunology (mL)	~60		~60	~50	~50		~60	~70	~50
Blood volume per visit (mL)	~69	~5	~65	~55	~55	~5	~65	~75	~50
Cumulative blood volume (mL)	~79	~84	~149	~204	~259	~264	~329	~404	~454

<sup>1Additional unscheduled visits may occur (for example: to repeat a blood test or for additional clinical review)

RECRef: 23/SC/0268 NIV001: A study of a new vaccine against Nipah Page 12 of 71 IRAS project ID: 1007433 Virus in adults aged 18 to 55

Virus in adults aged 18 to 55 Protocol V4.0, 16 AUG 2024

<sup>2eDiaries are remotely monitored in (near) real-time for the occurrence of grade ≥3 AEs and daily for non-completion³Minor differences in blood volumes may occur depending on the collection tubes and equipment used (~ = approximately); additional repeat blood draws may be required (for example: if there is a problem with the sample, abnormality in the results, or participant unwell). WOCBP: women of child bearing potential

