### 9.4.1 Vaccination Visits

Vaccination visits are held at the study site. The visit procedure for the vaccination visits, for both cohort 1 and cohort 2, will be as follows:

- Ensure that participant consent remains valid and verbally confirm continued consent
- Obtain and document interim medical history since the screening visit including medication
  use and other vaccinations, and check eligibility criteria, specifically temporary exclusion to
  vaccination, and perform a targeted physical examination (if required to reassess eligibility)
- Record temperature, pulse and blood pressure
- Perform highly sensitive urinary pregnancy test for females of childbearing potential (section 8.4); alternatively
- Perform blood draw (as per section 9.6)
- Administer vaccine or placebo by IM injection into the deltoid muscle (ideally the nondominant arm)

RECRef: 23/SC/0268 NIV001: A study of a new vaccine against Nipah Page 35 of 71 IRAS project ID: 1007433 Virus in adults aged 18 to 55

- Post-vaccination observation of volunteer for a minimum of 30 minutes following vaccine administration
- On the first vaccination visit (D0), participant is provided access and training to use the electronic diary (eDiary) using the participant's personal email address for the set-up
- Schedule next visit and re-iterate participant requirements such as completion of the eDiary entries
- On the subsequent vaccination visit, review of AEs and SAEs since the last visit

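### The exploratory anti-PF4 change has no pre-second-dose (V2) value and no named reference, so a rise after dose 2 can be judged only at group level against Group 1

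*Protocol*

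**What the plan says.** The table in Protocol section 6.1 has an exploratory objective, "To assess anti-PF4 antibody levels following vaccination", with the outcome measure "Change in anti-PF4 antibody level measured by ELISA". Its evaluation timepoints are D0, D14 and V2+14. V2 is not among them, and no reference value for the change is given.

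The neighbouring exploratory rows (immunological profiling and anti-vector immunity) leave their timepoints to the laboratory analysis plan. The anti-PF4 row fixes its own.

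The secondary G-specific ELISA in the same table does include the pre-second-dose visit. For Cohort 2 it reads "Cohort 2: D0, D14, D28, V2, V2+14, V2+28, V2+281", and the Cohort 1 list also contains V2.

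The footnote to the table makes the exploratory work optional ("These exploratory endpoints may be performed") and leaves room to extend it ("Further exploratory assays/analyses may be carried out").

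Tables 2 and 3 (sections 4.2 and 4.3) show about 50 mL of immunology blood at V2 in both cohorts. Section 9.4.1 lists the blood draw ahead of the injection, so that sample is pre-dose.

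**The concern.** A change after a dose is normally read against a value taken just before it. D14 minus D0 does this for dose 1. For dose 2 the listed earlier values are D0, taken before any vaccine, and D14, taken two weeks after the first dose. Neither shows the level on the day of the second injection.

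Suppose a two-dose recipient has a raised value at V2+14. Dose 2 may have caused it, a value already raised at D14 may have persisted, or the level may have risen between D14 and V2. Without a V2 value these explanations cannot all be separated in that person. Because the reference for the change is not named, two analysts could also report different quantities under the same label.

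Section 5.8.1 lists thrombosis with thrombocytopenia among the very rare reactions seen with the related COVID-19 vaccine and says "It is currently unknown whether these very rare reactions occur with other ChAdOx1 vaccines". That section does not mention PF4, so linking the assay to that risk is an inference, though a reasonable one. If the assay is meant to inform that question, an unusual value in one participant is what someone would want to date to a dose.

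**Working it through.** The Protocol gives no figure for the anti-PF4 objective. Its one design figure, in section 13.1.2, reproduces: 1 − 0.95^46 = 0.906, which is more than 90%. Nothing below depends on it.

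**Who is affected** (section 7.1)
- Two-dose recipients: 6 (Group A) + 20 (Group 2) = 26.
- Saline second injection after vaccine: 20 (Group 1). These can show dose-1 carry-over.
- Saline twice: 5 (Group 3). These had no first vaccine dose and cannot show carry-over.

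**Time gaps** (windows from Tables 2 and 3: D14 ±3, V2 at day 84 ±14, V2+14 ±3)
- D0 to V2+14: 84 + 14 = 98 days nominal; 70 + 11 = 81 to 98 + 17 = 115 with windows.
- D14 to V2, not observed for anti-PF4: 84 − 14 = 70 days nominal; 70 − 17 = 53 to 98 − 11 = 87 with windows.

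**What the three values can show in one participant with a raised V2+14**
- D14 not raised: simple persistence of a day-14 response is ruled out. A rise between D14 and V2 is not.
- D14 raised: persistence and a new rise after dose 2 cannot be told apart.
- With V2 added, either case can be read directly from V2+14 against V2.

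**What Cohort 2 can show on average.** Groups 1 and 2 are treated alike until V2 and are randomised. Group 1 at V2+14 therefore carries the dose-1 level plus saline, and Group 2 minus Group 1 at V2+14 estimates the average effect of dose 2.

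The approximate 95% half-widths below are in SD units of log anti-PF4, using a normal approximation and equal variances. The within-person correlation ρ is not in the Protocol and is assumed at 0.3 to 0.9.
- (a) Group 2 minus Group 1 at V2+14, unadjusted: 1.96 × √(2/20) = 0.62.
- (b) The same, adjusted for one earlier sample: (a) × √(1 − ρ²).
- (c) Difference between the groups in V2+14 minus V2: 1.96 × √(4(1 − ρ)/20).
- (d) V2+14 minus V2 within Group 2 alone: 1.96 × √(2(1 − ρ)/20).

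| ρ | (a) | (b) | (c) | (d) |
|---|---|---|---|---|
| 0.3 | 0.62 | 0.59 | 0.73 | 0.52 |
| 0.5 | 0.62 | 0.54 | 0.62 | 0.44 |
| 0.7 | 0.62 | 0.44 | 0.48 | 0.34 |
| 0.9 | 0.62 | 0.27 | 0.28 | 0.20 |

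Contrasts (a) and (b) are available without V2, with D0 or D14 as the earlier sample in (b). At the same ρ, the controlled change in (c) is no more precise than (b). Column (d) is narrower, but it is uncontrolled and equals the dose-2 effect only if levels would otherwise have stayed flat. So the main gain from V2 is a within-person reading, including in Cohort 1. Precision of the randomised contrast improves only if V2 correlates with V2+14 more strongly than D0 or D14 does.

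**The case against.** A reader might infer that a rise after dose 2 cannot be told from dose-1 carry-over at all. The documents do not support that. Group 1 is a concurrent, randomised measure of carry-over, sampled at the same visit. Section 13.1.1 rules out between-group testing but not side-by-side estimates with confidence intervals. Nor is the post-saline value in Group 1 a weakness: it is the control value.

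A reader might also infer that safety monitoring is compromised. It is not. Thrombosis with thrombocytopenia and thrombocytopenia are adverse events of special interest collected throughout (section 11.2 and the schedules), full blood counts are taken at V2 and V2+14, and no holding rule in section 11.24 uses anti-PF4.

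The strongest remaining defence is that the objective promises only levels after vaccination, not attribution to a particular dose in a particular person. Change from the vaccine-naive D0 value fits that wording and keeps any lasting dose-1 elevation in view, which V2+14 minus V2 alone would subtract out. The endpoint is also optional, and V2 could be assayed under the footnote's allowance for further work.

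Most of this stands, and it sets the severity and shapes the fix. It does not supply a dose-2 baseline if the row is run as written, and it does not help Cohort 1, which has no concurrent control. Relying on a later decision also carries some risk: under section 9.6.4, remaining samples from participants who decline the Biobank are destroyed after the required storage period.

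**Conclusion.** The point holds in a limited form. The plan fixes a change measure without a V2 value and without naming its reference, so no dose-2 change from a pre-dose value can be calculated for any of the 26 two-dose recipients. In Cohort 2 the dose-2 effect remains estimable as a group average against Group 1, with a 95% half-width of about 0.62 SD unadjusted. What is missing is full attribution within a participant, because neither a late rise between D14 and V2 nor persistence of a value already raised at D14 can be excluded. For the six Cohort 1 participants even the group-level route is closed.

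Severity is low, since the endpoint is exploratory, optional and descriptive. The conclusion about what can be identified rests only on the listed timepoints and the allocation. The half-widths rest on the assumed correlations and the normal approximation.

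**What to change.** Add V2 (pre-injection) to the anti-PF4 timepoints in section 6.1 for both cohorts, and name the reference for each change:
- dose 1: D14 minus D0;
- dose 2: V2+14 minus V2;
- overall: V2+14 minus D0, kept so that persisting dose-1 elevation stays visible.

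Present all three by group. Group 1 then shows carry-over, and Group 3 shows drift without vaccine.

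The cost is one more ELISA sample per participant, about 51 if everyone attends V2 (more wells if run in replicate), plus one table entry and a sentence of definition. The sample comes from the immunology blood already scheduled at V2, so no visit or blood draw is added.

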#### 7 STUDY DESIGN

This is a participant-observer blind, randomised, placebo-controlled, first-in-human phase I trial to assess the safety, tolerability and immunogenicity of one or two administrations of an intramuscular (IM) ChAdOx1 NipahB vaccine in healthy adults aged 18 to 55 years. There will be an initial unblinded lead-in cohort (cohort 1) of 6 participants, followed by a participant-observer blind cohort of 45 participants, 4:4:1 randomised to single dose ChAdOx1 NipahB, two-dose ChAdOx1 NipahB, or placebo, respectively (cohort 2).

Volunteers will be recruited and vaccinated at the designated study site.

#### 7.1 Study Groups

Cohort	Group	Number of Participants	Intervention 1 (Week 0)	Intervention 2 (Week 12)	Follow-up Period
1	А	6	5 × 10  vp ChAdOx1 NipahB	5 × 10  vp ChAdOx1 NipahB	1 year
	1	20	5 × 10  vp ChAdOx1 NipahB	Saline placebo	1 year
2	2	20	5 × 10  vp ChAdOx1 NipahB	5 × 10  vp ChAdOx1 NipahB	1 year
	3	5	Saline placebo	Saline placebo	1 year

#### 7.2 Definition of Start and End of Trial

The start of the trial is defined as the date of the first vaccination of the first volunteer. The end of the trial is defined as the point when all assays providing data for primary and secondary endpoints have been completed.

#### 7.3 Trial Duration

The total duration of the study will be 12 months from the day of enrolment for each volunteer. Participants will be considered enrolled in the trial once they have been randomised.

### 7.4 Group Allocation

The first 6 participants recruited to the trial will be enrolled to cohort 1. These 6 individuals will be non-randomly allocated to group A, an open-label lead-in group.

All subsequent participants (n=45) will be recruited into cohort 2 and randomly allocated to either group 1, 2 or 3 using a 4:4:1 randomisation ratio, respectively. Recruitment into cohort 2 will only proceed following the safety review detailed in section 11.22.

RECRef: 23/SC/0268 NIV001: A study of a new vaccine against Nipah Page 27 of 71 IRAS project ID: 1007433 Virus in adults aged 18 to 55

Virus in adults aged 18 to 55 Protocol V4.0, 16 AUG 2024

